1.0 BACKGROUND – POSTURAL TACHYCARDIA SYNDROME

1.1 Postural Tachycardia Syndrome

Postural Tachycardia Syndrome (POTS) is a chronic form of orthostatic intolerance marked by a significant and sustained increase in heart rate (HR) upon positional change from supine to standing (≥ 30 beats/min [bpm])¹ in the absence of orthostatic hypotension ($\geq 20/10$ mmHg decrease)². Symptoms must be present for ≥ 6 months³ and other causes of orthostatic tachycardia must be ruled out¹. Individuals with POTS report orthostatic symptoms including palpitations, light-headedness, dizziness, chest pain, and mental clouding, which improve on recumbence². 80-85% of individuals diagnosed with POTS are women age 13-50³. Current treatment of POTS involves pharmacological and non-pharmacological intervention including salt and fluid loading, exercise, and physical countermaneuvers⁴.

1.2 Physiology

Upon standing, approximately 500 mL of blood immediately redistributes from the thorax down to the abdomen, buttocks and legs². Blood return to the heart is decreased⁵ and therefore stroke volume and arterial pressure decreases². This leads to sympathetic activation as the baroreceptors sense less pressure². In a healthy individual, HR initially increases 10-20 bpm, and the systolic blood pressure (BP) decreases by approximately 5 mmHg². However, in an individual with POTS, this compensatory mechanism is impaired and HR will increase by ≥ 30 bpm and remain at this elevated rate for the duration of standing². In some individuals with POTS, upon standing cerebral blood flow velocity decreases⁵. In other individuals, oscillation of cerebral blood flow due to failure of cerebral autoregulatory mechanisms is observed⁶.

2.0 COMPRESSION GARMENTS

2.1 Compression Garment Mode of Action

Lower extremity compression garments provide pressure to the blood vessels in the legs, thighs and abdomen which can minimize blood pooling and lead to improved blood return to the heart⁴.

2.2 Use of Compression Garments in Postural Tachycardia Syndrome

A study of compartmental fluid shifts on head up tilt found that in POTS patients, splanchnic blood volume increased on tilt⁷. In 2 subsets of POTS patients, this increase in blood volume was significant when compared to the healthy control group⁷. As well, blood volume in the pelvis and leg also increased upon head up tilt⁷. Interesting, in one subset of POTS patients, blood flow to the splanchnic region also increased significantly on 70° head up tilt⁷. GL Heyer evaluated the use of compression in children and teens with POTS⁴. They completed 3 head-up tilt table tests (HUTT), the first without compression, the second using the Zoex non-inflatable antishock garment (20-40 mmHg to the abdomen) and the third without compression⁴. The Zoex non-inflatable antishock garment has 6 flexible straps that fasten tightly around the legs, thigh, waist, and abdomen as well as a thin bladder on the attached to the abdominal straps. This bladder compresses the abdominal wall and the garment provides overall compression of 20-40 mmHg⁴. It was shown that the compression garment reduced orthostatic tachycardia and

orthostatic symptoms on tilt, and that both the tachycardia and symptoms returned on the third tilt test, when no compression was applied⁴. Despite the evidence of blood pooling in the abdomen, pelvis and leg,⁷ and these promising findings with a non-commercial compression garment, there is relatively little other research indicating the benefits of abdominal and lower extremity compression garments in POTS. There are no data on the use of these compression garments in adult POTS patients with upright stress. Further, it is not known where compression is most effective in an individual with POTS (e.g. abdomen, thigh, lower leg, combination of these).

2.3 LifeWrap Non-Pneumatic Anti-Shock Garment (NASG)

The LifeWrap Non-Pneumatic Anti-Shock Garment (NASG)⁸ is used as a treatment for postpartum hemorrhage in developing countries, and is comprised of neoprene fabric with a compression ball and Velcro closures that can be adjusted for use⁸. This garment consists of 3 leg segments and 2 pelvic/abdominal segments, and applies pressure to the external body surface in order to maintain adequate blood flow to the heart, lungs and brain, countering the effects of hypovolemic shock⁸. This garment is a Health Canada class I medical device.

2.4 Significance

There are no approved medications for use in POTS and patients are usually managed with a combination of off-label medications and non-pharmacological treatments³. Compression garments are often prescribed as one of these non-pharmacological management strategies³. However, there is no data to validate their efficacy, and also no data to determine which type of compression is most beneficial (e.g. lower leg only, abdomen only, combination) in adults. We will endeavour to complete a 4-way randomized crossover study of head up tilt tests (HUTTs) with compression applied by the LifeWrap NSAG in an attempt to demonstrate decreased orthostatic tachycardia and increased orthostatic tolerance in individuals with POTS. If successful, this study could provide needed evidence that compression in POTS is a successful non-pharmacological treatment modality, and as well, what type of compression is the most beneficial to patients with this syndrome. These findings could rapidly translate to the clinical setting and improve patient care.

3.0 HYPOTHESIS

3.1 Hypothesis

Full abdominal and lower extremity compression will reduce orthostatic tachycardia (lower HR increase on standing) and orthostatic symptoms in patients with POTS.

4.0 INCLUSION/EXCLUSION CRITERIA:

Inclusion Criteria:

- Physician diagnosis of Postural Tachycardia Syndrome (POTS)
- Age 18-60 years
- Male and Female
- Able and willing to provide informed consent
- Ability to travel to Libin Cardiovascular Institute of Alberta Autonomic Testing Lab at the University of Calgary, Calgary, AB.

Exclusion Criteria:

- Overt cause for postural tachycardia, i.e., acute dehydration
- Participants with somatization or severe anxiety symptoms will be excluded
- Pregnant
- Inability to tolerate compression garment for the duration of the study
- Other factors which in the investigator's opinion would prevent the participant from completing the protocol, including poor compliance during previous studies

5.0 ENROLLMENT, RANDOMIZATION and BLINDING

5.1 Recruitment

Patients will be recruited from the Calgary Autonomic Investigation and Management Clinic, and the practices of Drs. [name], [name], and [name], including past research study participants. We will also recruit participants who contact us directly about their interest in our studies.

5.2 Randomization:

Each study participant will complete 4 HUTT on a single day:

- i. one wearing the LifeWrap NASG Garment with all segments fastened;
- ii. one wearing the LifeWrap NASG Garment with the lower leg components fastened;
- iii. one wearing the LifeWrap NASG with the abdominal and pelvic components fastened; and
- iv. one without the garment entirely.

The order of the interventions will be randomized to account for diurnal variation of HR and BP observed in POTS⁹, and any possible training effect with repeated HUTT. Randomization will be performed using a pre-prepared randomization table.

5.3 Blinding

None. It will not be possible to blind the subject to the compression intervention.

6.0 STUDY PROCEDURE

6.1 Holding Pre-Existing Medications

Since this will be a crossover study and each subject will act as their own control, we will not need to preclude the use of medications for this protocol. This will also make the study more clinically relevant and generalizable, as compression would most likely be recommended to patients in addition to medications. We will make note of the medications being used by each participant at the time of the study.

6.2 Study Design

6.2.1 General

This study will utilize a single-day, 4-way randomized crossover design, with assessments of HUTT with:

- i. no compression;
- ii. lower leg compression only;
- iii. abdomen/pelvic compression only; and
- iv. both abdomen/pelvic and lower leg compression.

The study will be conducted on a tilt table in a human physiology research and procedure room. Each intervention phase in the protocol will involve a baseline assessment period of 10 minutes followed by a 10 min HUTT (80 degrees). There will be a 20 min recovery periods between each HUTT. The study will take approximately 4 hours.

6.2.2. Interventions

The Lifewrap NSAG Compression Garment has been developed to treat postpartum hypovolemic shock and provides external compression to the abdomen, pelvis and lower extremities⁸. A pressure sensor will be used to ensure standardized compression application throughout the study.

6.2.3 Instrumentation

- The patient will be instrumented in a fasting state on an empty bladder. Patients will be allowed to drink water on the morning of study.
- The entire study will take place with the subject on the tilt table (supine or tilted)
- The skin electrodes will be applied for continuous ECG and HR monitoring.
- BP will be monitored continuously using a finger volume clamp method (Nexfin, BMEYE Inc.) and calibrated with intermittent brachial cuff measurements (Vital-Guard 450C Patient Care Monitor, IVY Medical).
- From the continuous BP waveform, we can get an estimate of stroke volume, cardiac output, and systemic vascular resistance (Modelflow).
- Middle cerebral blood flow velocity will be assessed using Spencer Technologies ST³ Digital Transcranial Doppler System Model PMD150 (TCD).
- Oxygen saturation will be assessed from a finger probe.
- End-tidal CO₂ will be measured using nasal prongs.

6.2.4 Study Day

- The participant will be asked about co-morbid disorders, and current pharmacological and non-pharmacological treatments of POTS
- The participant will be instrumented in a fasting state (aside from water as needed).
- The compression garment will be worn, but not initially strapped tight. The compression garment will be tightened around segments as determined by the order of randomization
- Participant will be strapped onto the tilt table (for their safety)
- Supine for 20 minutes prior to baseline data collection
- For each intervention:
 - Physiological signals will be digitally sampled throughout the study
 - 10 minute baseline data collection (supine)
 - Table will be tilted up to 80 degrees (head up) for 10 minutes
 1. Tilt will be terminated early if the patient has syncope or if the patient requests that the table be returned to the supine position. If the tilt is terminated early, the duration of the tilt will be recorded.
 2. Symptoms will be assessed using the brief Vanderbilt Orthostatic Symptom Score before the end of tilt.
 - Table will be returned to the supine position

- The next compression garment intervention will be applied, removed or fastening modified depending on randomization scheme
- After completion of the 4th intervention, the study is over
 - The compression garment will be removed.
 - Study participant will be de-instrumented

6.3 Study Outcome Measures

- The primary outcome measure will be the magnitude of Δ HR from supine to head up tilt (max between 5-10 min of HUTT) for each intervention
- Secondary outcome measures for each intervention will include the peak standing HR between 5-10 min HUTT, VOSS Symptom Rating at end of each 10min HUTT, BP, advanced hemodynamics & CBF at peak standing HR during 5-10 min HUTT.

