7.0 STATISTICAL CONSIDERATIONS

7.1 Primary Analysis

The primary analysis will compare the magnitude of Δ HR from supine to head up tilt (max between 5-10 min of HUTT) when the participant is wearing the LifeWrap NASG with full compression applied compared to when the patient has no compression applied. The comparison will use a paired t-test (or a Wilcoxon Signed-Rank test if the data are non-normally distributed).

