7.2 Secondary Analysis

The secondary analyses will compare the magnitude of Δ HR from supine to head up tilt (max between 5-10 min of HUTT) with partial compression to no compression and to full compression. Other secondary analyses will include patient reported orthostatic symptoms on tilt with different compression garment configurations, and assessments of other hemodynamic parameters in different garment configurations as well as a regression analysis of orthostatic heart rate and orthostatic symptoms. We will also consider biological sex differences in response to the compression garment. Additionally, co-morbid medical conditions and the medications each participant is prescribed will be evaluated to investigate possible differences in response to the compression garment.

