8.0 RISKS and INCOVENIENCES

BP cuff: Some may find it uncomfortable to hold their arms with an inflated cuff placed around the forearm, or finger, in a relatively fixed position, or have the cuff inflated frequently.

Electrodes: Sticky patches will be put on your chest and your limbs to record electrical activity from your heart. This might be uncomfortable to you. This can occasionally cause a rash.

Compression Garments: The LifeWrap garment may be uncomfortable to wear.

Tilt-table test (HUTT): There might be light-headedness, dizziness, tremor, headache or nausea during the tilt table test. These symptoms usually resolve rapidly upon lowering of the table.

Transcranial Doppler (TCD): Ultrasound gel will be applied which may cause a rash. The Doppler probe will be in direct contact with the head, which may be uncomfortable. The headband/apparatus will be snug, but there will be opportunities to loosen it off during the recovery periods. Extended use of TCD at a high power may cause tissue heating, however we will keep the TCD at low power, and turn off the data acquisition during recovery periods.

Syncope: A small portion of individuals may experience fainting (syncope) while tilted upright. We will continuously monitor your blood pressure and heart rate and lower you immediately if you faint or request to be lowered. If you faint, you may chose to stop the study or continue with the next tilt table test, if you feel well and are willing.

We cannot foresee any other risks, but there may be previously unknown or unforeseen risks.

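### Does the lack of a stated VOSS value for a tilt stopped early undermine the planned symptom comparison?

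*Combined protocol and SAP*

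**What the plan says.** The hypothesis in section 3.1 has a heart-rate part and a symptom part: "Full abdominal and lower extremity compression will reduce orthostatic tachycardia (lower HR increase on standing) and orthostatic symptoms in patients with POTS". VOSS is the only symptom measure named. Section 6.3 makes it a secondary outcome, timed as "VOSS Symptom Rating at end of each 10min HUTT".

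The list of study-day procedures in section 6.2.4 has two numbered items under the tilt. The first says "Tilt will be terminated early if the patient has syncope or if the patient requests that the table be returned to the supine position" and adds "If the tilt is terminated early, the duration of the tilt will be recorded". The second, directly after it, says "Symptoms will be assessed using the brief Vanderbilt Orthostatic Symptom Score before the end of tilt". Section 8.0 tells participants that staff will "lower you immediately if you faint or request to be lowered", that a small share may faint, and that someone who faints may go on to the next tilt.

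Section 7.2 plans an analysis of "patient reported orthostatic symptoms on tilt with different compression garment configurations" and a regression of symptoms and heart rate. It names no test for symptoms and no rule for a short tilt. For the primary outcome, section 7.1 names a paired t-test, or "a Wilcoxon Signed-Rank test if the data are non-normally distributed".

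**The concern.** Sections 6.3 and 6.2.4 agree for a tilt that runs its full 10 minutes. For a shorter one they can be read apart: section 6.3 could mean that there is no score, and section 6.2.4 that there is a score after less time upright. After syncope the participant is lowered at once, so the question may not have been asked, and an unasked score cannot be rebuilt later. Because a participant may continue after fainting, one person can have one short tilt and three complete ones, which puts the problem inside the paired comparison.

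The choice of rule could then matter in either direction. Suppose a participant stops at 3 minutes without compression and completes 10 minutes with full compression at the same score. At face value that pair shows no benefit, although time upright rose by 10 − 3 = 7 minutes. Conversely, section 8.0 warns that the garment may be uncomfortable. If discomfort led to stops under full compression and those pairs were dropped, the symptom result would describe only those who could finish. With 40 participants, at least one would be affected with probability 1 − 0.98^40 = 0.55 if the true share is 2%, and 1 − 0.95^40 = 0.87 if it is 5%.

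**Working it through.** **Inputs.** From section 7.3: difference 10 bpm, SD 15 bpm, two-sided 0.05, 90% power, 26 needed, 40 enrolled. The documents give no VOSS effect, no VOSS spread and no early-stop rate. Stop rates of 5%, 10% and 20% are therefore assumed, and the symptom effect is set equal to the heart-rate effect, 10/15 = 0.67 SD of the paired difference.

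**1. The plan's own figure.** Normal approximation: n = (15 × (1.960 + 1.282)/10)² = 23.6, so 24. The exact paired t-test gives 89.2% power at 25 and 90.4% at 26, so 26 reproduces. At 40 the power is 98.4%. This calculation concerns heart rate and does not depend on VOSS.

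**2. What is unwritten.** In section 6.2.4 the scoring instruction follows the early-stop provision and is not restricted to completed tilts. Read naturally, the score is taken before the table comes down, whenever that is. The 10 minutes in section 6.3 can be read as the name of the procedure, as in section 6.2.1. Two things remain unwritten: the score when syncope prevents asking, and how a short-tilt score is analysed.

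**3. Number of pairs.** As an upper bound on loss, suppose every short tilt lost its score and stops were independent across tilts. Full-versus-none pairs left are 40 × (1 − q)²: 36.1 at q = 5%, 32.4 at 10%, 25.6 at 20%.

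**4. Stops only under full compression, unrelated to benefit.** Simulation of 20,000 trials with d = VOSS(none) − VOSS(full) ~ N(0.667, 1), N = 40. Entries are the chance of a significant benefit. With no stops it is 0.98 by either test.

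| Share stopping | Drop the pair (t-test) | Stopped tilt ranked worst (signed-rank) |
|---|---|---|
| 5% | 0.98 | 0.80 |
| 10% | 0.97 | 0.47 |
| 20% | 0.95 | 0.07 |

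The mean in the remaining pairs stays at 0.67 SD. The fall in the right-hand column comes from worst-rank scoring, which the plan does not propose and which answers a different question (symptoms and stopping combined).

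**5. Stops only without compression, correlated 0.5 with benefit.** After dropping pairs, the mean is 0.667 − 0.5 × φ(z)/(1 − q), where z is the upper-q normal point.

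- 10%: 0.667 − 0.5 × 0.175/0.90 = 0.57 SD.
- 20%: 0.667 − 0.5 × 0.280/0.80 = 0.49 SD.
- Simulated power at 5%, 10% and 20%: 0.96, 0.93 and 0.81.

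The benefit is understated, not created. A separate model in which high symptoms trigger stops in either condition (true effect 0.50 SD, within-person correlation 0.5 to 0.7) gives complete-pair effects of 0.47–0.48, 0.44–0.46 and 0.40–0.44 SD when 5%, 10% and 20% of uncompressed tilts stop. The direction is the same.

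**6. Would a prespecified worst-rank check help?** Take a rule that claims symptom benefit only if the scores as taken and a worst-rank analysis both succeed, with equal scores at the stop:

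- Uncompressed stops at 10% and 20%: 0.93 and 0.81, no gain over dropping pairs.
- Full-compression stops at 5%, 10% and 20%: 0.80, 0.47 and 0.07.

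The rule takes the worse result each way.

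**The case for a change.** The strongest case for a change is that collection cannot be repaired afterwards. A score not asked before syncope is gone, a 3-minute score and a 10-minute score are not the same measurement, and the trial is unblinded (section 5.3), so choosing a rule after seeing the data leaves room for a favourable choice. The enrolment of 40 adds numbers but does not remove bias.

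Part of this stands. The syncope score and the analysis rule are indeed unwritten. The independence assumed in step 4 also matters: if those who stop under full compression were the ones who benefit least, dropping them would overstate the effect. With the same correlation of 0.5 and 10% stopping, the mean would be 0.667 + 0.5 × 0.175/0.90 = 0.76 SD.

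What weakens it is how far the assumptions must be pushed. Section 4.0 excludes people who cannot tolerate the garment for the study's duration. That does not rule out stops under compression, but it makes 10–20% there, with none in the uncompressed tilt, an extreme case. A stop for garment discomfort also need not track orthostatic symptoms. Section 8.0 expects fainting in only a small share, and tilt duration is recorded, so short tilts can be identified and reported in any case. A worst-rank analysis with power to block the claim would rest on unblinded request stops, and would no longer be a mere sensitivity analysis.

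**Conclusion.** No change to the plan follows. The gap is limited to the score after syncope and the handling of short-tilt scores, for a secondary outcome in a study that section 7.3 describes as proof of concept. An analyst can reasonably use the score taken when the tilt ended and report early stops by condition from the recorded durations.

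The conditional figures do not show that the plan as written misleads. With a 0.67 SD effect and N = 40, dropping pairs keeps power at 0.95 or more for full-compression stops of up to 20% that are unrelated to benefit. For uncompressed stops correlated 0.5 with benefit, it gives 0.96, 0.93 and 0.81 at 5%, 10% and 20%, with the benefit understated. The stop rates, the correlation and the symptom effect are all assumptions; the true effect on VOSS is unknown, and it is nil if nobody stops early. The sample size of 26, enrolled as 40, is unaffected. A binding worst-rank rule would be a trade-off with a real cost and no gain in the scenarios examined.

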7.0 STATISTICAL CONSIDERATIONS

7.1 Primary Analysis

The primary analysis will compare the magnitude of Δ HR from supine to head up tilt (max between 5-10 min of HUTT) when the participant is wearing the LifeWrap NASG with full compression applied compared to when the patient has no compression applied. The comparison will use a paired t-test (or a Wilcoxon Signed-Rank test if the data are non-normally distributed).

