7.3 Sample Size Calculation

Since this is a proof of concept study, there is no preliminary data about the effect of compression on orthostatic HR change in adults. In a pediatric study⁴, the mean orthostatic HR change upon the addition of abdominal and leg compression was about 25bpm. Orthostatic tachycardia is physiologically greater in children and decreases with increasing age, so a more conservative assumption is required. A clinically meaningful reduction in orthostatic tachycardia of 10 bpm would be clinically significant. We estimate a standard deviation of about 15 bpm for our sample. With the aforementioned assumptions for a paired test of continuous data and a 0.05 two-sided significance level, a sample size of 26 POTS patients would allow for 90% power to detect this difference. To account for study withdrawal and dropout we will enroll **40 POTS patients in total**.

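### Tilt order is randomised against time effects, but the primary paired test has no period term: a possible loss of precision, not of validity

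*Combined protocol and SAP*

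**What the plan says.** Section 5.2 gives the reason for randomising: "The order of the interventions will be randomized to account for diurnal variation of HR and BP observed in" POTS, together with "any possible training effect with repeated HUTT". Both are effects of when a tilt takes place, that is, period effects. On method it says only: "Randomization will be performed using a pre-prepared randomization table". It does not state which sequences are used or whether each condition appears equally often in each position.

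Section 7.1 tests full against no compression: "The comparison will use a paired t-test (or a Wilcoxon Signed-Rank test if the data are non-normally distributed"). Section 7.2 compares ΔHR "with partial compression to no compression and to full compression" and names neither a method nor a period term.

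Two design facts bear on the point. Section 6.2.4 gives every tilt its own supine baseline of 10 minutes, and section 6.2.1 says "There will be a 20 min recovery periods between each HUTT".

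For the sample size, section 7.3 says "We estimate a standard deviation of about 15 bpm for our sample". It does not say whether that figure includes variation between periods.

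**The concern.** The design names a nuisance factor and the analysis then omits it. Randomising order stops time from favouring one condition on average, but it does not take time out of the data. One participant may have full compression first and none last, and another the reverse. If ΔHR drifts over the session, their paired differences move in opposite directions, and the paired test treats that spread as noise.

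Only one kind of drift matters. Each tilt has its own baseline, so a shift that raises supine and tilted heart rate equally cancels out of ΔHR. What remains is drift in the orthostatic response itself. A cycle is 10 + 10 + 20 = 40 minutes, so the first and last tilts are 3 × 40 = 120 minutes apart, long enough for either mechanism named in section 5.2 to act.

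At stake are the width of the primary confidence interval and some power. The direction of the estimate and the type I error guarantee are not at risk.

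**Working it through.** **Inputs.** From section 7.3: effect 10 bpm, SD 15 bpm, two-sided 0.05, 26 participants for 90% power, 40 enrolled. From section 5.2: four tilts in random order. Assumed, because the documents give no figure: a linear drift in ΔHR of b bpm per tilt, with b = 0, 2, 3, 5. That is 0, 6, 9, 15 bpm from first to last tilt.

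**Step 1: the plan's own figure.** Taking 15 bpm as the SD of paired differences, a noncentral-t calculation at n = 26 gives 90.4% power, so the stated sample size reproduces.

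**Step 2: variance added by drift, unrestricted order.** Two distinct positions out of four are 1 apart in three of six pairs, 2 apart in two and 3 apart in one. The mean squared gap is (3×1 + 2×4 + 1×9)/6 = 20/6 = 10/3. The variance of a paired difference is therefore 225 + (10/3)b².

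**Step 3: case 1, the 15 bpm excludes drift.**

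| b | SD of difference | Paired power, n = 26 | Paired power, n = 40 |
|---|---|---|---|
| 0 | 15.0 | 90.4% | 98.4% |
| 2 | 15.4 | 88.8% | 97.9% |
| 3 | 16.0 | 86.6% | 97.1% |
| 5 | 17.6 | 79.7% | 94.0% |

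The alternative was simulated: condition and four-level period, within participant, with small-sample-corrected clustered standard errors (CR2, Satterthwaite degrees of freedom) and residual SD 15/√2 = 10.6. Its power is about 89% at n = 26 and 98% at n = 40 for every b. At n = 26 it loses about 1 point at b = 0, is level at b = 2, and gains about 2.5 points at b = 3 and 9 at b = 5. At n = 40 it gains about 1 point at b = 3 and 4 at b = 5. Type I error with unrestricted order, at b = 0 and b = 5, is 4.8–5.0% for the paired test and 4.9–5.1% for the model.

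**Step 4: break-even.** With no drift, the average 95% CI half-width at n = 26 is 6.01 bpm paired and 6.15 bpm for the model. Because 225/(10/3) = 67.5, the paired width grows as √(1 + b²/67.5). Setting 6.01·√(1 + b²/67.5) = 6.15 gives b of about 1.8. At n = 40, 4.77·√(1 + b²/67.5) = 4.835 gives b of about 1.4.

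**Step 5: case 2, the 15 bpm already includes drift.** The planned 90.4% stands. The drift-free SD is √(225 − (10/3)b²) = 14.5, 14.0, 11.9 at b = 2, 3, 5. The model then has 91.0%, 93.3%, 98.2% power at n = 26, with half-widths of 5.96, 5.71, 4.91 bpm against about 6.0 paired. Here the omission only forgoes a gain.

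**Step 6: case 3, a balanced table.** In a four-sequence Williams square with n = 40, drift cancels from the mean difference but still enters its estimated standard error. The mean squared gap is 2.5 for four of the six condition pairs and 5 for the other two. The ratio of estimated to true standard error is √((225 + 2.5b²·40/39)/225), or the same with 5 in place of 2.5. That gives 1.05 or 1.10 at b = 3 and 1.13 or 1.25 at b = 5. Simulated type I error of the paired test falls to 4.2% or 3.3% at b = 3 and 2.8% or 1.5% at b = 5, so the test becomes conservative.

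**The case against.** The best defence is that the design already deals with time. Order is randomised for this purpose, the paired test is valid after it, and section 7.3 powers a paired test. The drift is also unsupported: the diurnal variation cited in section 5.2 is in heart rate and blood pressure, and the separate baselines remove any additive part. The only direct support for drift in ΔHR is the possible training effect. A drift of 5 bpm per tilt means 15 bpm over the session, 1.5 times the 10 bpm target effect. Enrolling 40 absorbs most of the loss: at b = 3, paired power exceeds 90% with as few as 30 completers. The 9-point gain needs b = 5 and also the loss of 14 of 40 participants in a one-day study. Finally, the replacement changes more than a period term. It admits participants with missing tilts and moves the signed-rank fallback to a sensitivity analysis, while all the figures assume complete, normal data.

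Much of this stands. The analysis is valid as written, the drift size is unknown, and the loss with 40 completers is small. These facts set the weight of the point but do not remove it. Section 5.2 itself treats time effects as likely enough to design against, and the adjustment uses tilts that are collected anyway. With complete data the random-effect and within-participant forms of the model give the same contrast, because every participant has each condition and each period once. They can differ when tilts are missing, which is a reason to specify the model in advance. Keeping the paired and signed-rank tests as sensitivity analyses covers the concern about non-normality.

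**Conclusion.** The concern holds, as a matter of precision only. The primary paired test omits a factor that section 5.2 names. The estimate stays unbiased and type I error is not inflated: it is nominal under unrestricted order and below nominal under a balanced table. The cost is under 2 points of power at 26 completers for drift up to 2 bpm per tilt, about 4 points at 3 (90.4 − 86.6) and about 11 at 5 (90.4 − 79.7). With 40 completers, paired power is about 94% or more in every case shown.

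This rests on linear drift common to all participants, 15 bpm being the SD of paired differences, order truly randomised, and missing tilts not depending jointly on period and condition. If a balanced table stops at a number not divisible by four, a small shift remains: about 0.2 bpm at b = 2 and 0.6 bpm at b = 5 in simulation at n = 26, with type I error still below 5%. This is an inexpensive improvement to consider, not a flaw that undermines the trial.

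**What to change.** In section 7.1, take the primary estimate of full minus no compression, with its 95% CI, from a linear model of ΔHR on all available tilts. Use condition (four levels) and period (1 to 4) as fixed effects, participant as a random effect, and small-sample-corrected standard errors clustered by participant. Keep the paired t-test and the signed-rank test as sensitivity analyses. In section 7.2, take the partial-compression ΔHR contrasts from the same model. As an optional clarification, section 5.2 could state whether the table is balanced over positions.

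The cost is SAP wording, with no extra data or participants. With no drift and unrestricted order, the interval is about 2.5% wider at n = 26 (half-width 6.15 against 6.01 bpm) and about 1.5% wider at n = 40. With a balanced table at n = 40 it is no wider (4.77 bpm for both). The model does not correct for informative early stopping, such as after syncope, and a common period term does not remove drift that differs between participants.
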